### **3.3 Safety**

Safety and tolerability will be assessed in terms of adverse events (AEs) (including serious adverse events [SAEs]), deaths, laboratory data, vital signs, electrocardiograms (ECGs) and exposure. These will be collected for all patients. Data from all cycles of treatment will be combined in the presentation of safety data. ‘On treatment’ will be defined as assessments between date of start dose and 90 days following discontinuation of IP (i.e., the last dose of MEDI4736 monotherapy, MEDI4736 + tremelimumab combination therapy, or SoC) regardless of re-treatment period. For AEs, on treatment (or treatment-emergent AEs) will be defined as any AEs that started after dosing or prior to dosing and which worsens following exposure to the treatment. If an AE is not worse than the baseline (pre-dose) severity, then it will not be classified as TEAE.

Safety analysis set will be used for reporting of safety data.

#### **3.3.1 Adverse events (AEs)**

AEs and SAEs will be collected from the time of signature of informed consent throughout the treatment period and up to 90 days after the last dose of IP (MEDI4736 + tremelimumab, MEDI4736, or SoC) or until initiation of another therapy (excluding palliative radiation as anti-cancer therapy) regardless of whether the AE occurred during re-treatment with tremelimumab or not. Any AE occurring before treatment with IP will be included in the data listings but will not be included in the summary tables of AEs.

The Medical Dictionary for Regulatory Activities (MedDRA) dictionary will be used to code the AEs. AEs will be graded according to the National Cancer Institute Common Terminology Criteria for AEs (CTCAE Version 4.03 or higher).

#### **AEs of special interest (AESIs)**

Adverse events of special interest (AESIs) are events of scientific and medical interest specific to the further understanding of the MEDI4736 and tremelimumab safety profile and require close monitoring and rapid communication by the Investigator to the Sponsor. MEDI4736 and tremelimumab AESIs may be serious or non-serious. The rapid reporting of these AESIs allows ongoing analysis of these events in order to characterize and understand them in association with the use of these IPs.

Currently, these AESI's have been identified in the CSP as Diarrhea/Colitis and intestinal perforation, Pneumonitis/ILD, hepatitis/transaminase increases, Endocrinopathy (i.e. Events of hypophysitis/hypopituitarism, adrenal insufficiency, and hyper- and hypothyroidism and type I diabetes mellitus), Neuropathy/neuromuscular toxicities (eg Guillain-Barre and myasthenia gravis), Rash/Dermatitis, Nephritis/blood creatinine increases, Pancreatitis/serum lipase or amylase increases, myocarditis, myositis/polymyositis and other inflammatory responses that are rare/less frequent with a potential immune-mediated aetiology including, but not limited to, pericarditis, sarcoidosis, uveitis and other events involving the eye, skin, haematological and rheumatological events. .

An AstraZeneca medically qualified expert, after consultation with the Global Patient Safety Physician, has reviewed the AEs of interest and identified which preferred terms contribute to each AESI. A further review will take place prior to database lock to ensure new terms not already included in the older MedDRA version are captured within the categories for the new higher MedDRA version. The list will be provided by AZ prior to database lock.

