anemia (13%), neutropenia (22%), and thrombocytopenia (11%) with sepsis seen in 9 of 222 patients in the EXTREME group. Additionally, cetuximab-specific toxicities were observed, with Grade 3 skin reactions reported in 9% of patients and Grade 3 or 4 infusion-related reactions reported in 3% of patients ([Vermorken et al 2008](#)). While an 80% dose intensity was noted with the regimen as a whole, in reality, this regimen can only be effectively delivered to younger, fitter patients with a 0 to 1 Eastern Cooperative Oncology Group (ECOG) performance status. Unfortunately, the majority of patients diagnosed with head and neck cancer are older with a median age of 62 and have multiple comorbidities as a result of prior alcohol and tobacco use, including compromised cardiac and pulmonary function. Furthermore, as a result of therapy for this disease, such as radiation and/or surgery along with the disease itself, many also have compromised nutritional status that further makes delivering aggressive therapy with a favorable outcome difficult.

This population is therefore in need of therapies that are not only more efficacious in offering a longer survival benefit or even cure but can also be delivered with less toxicity than traditional chemotherapy regimens such as EXTREME.

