AESIs for MEDI4736 +/- tremelimumab include but are not limited to events with a potential inflammatory or immune-mediated mechanism and which may require more frequent monitoring and/or interventions such as steroids, immunosuppressants, and/or hormone replacement therapy. These AESIs are being closely monitored in clinical studies with MEDI4736 monotherapy and combination therapy. An immune-related adverse event (irAE) is defined as an AE that is associated with drug exposure and is consistent with an immune-mediated mechanism of action and where there is no clear alternate etiology. Serologic, immunologic, and histologic (biopsy) data, as appropriate, should be used to support an irAE diagnosis. Appropriate efforts should be made to rule out neoplastic, infectious, metabolic, toxin, or other etiologic causes of the irAE.

If the Investigator has any questions in regard to an AE being an irAE, the Investigator should promptly contact the Study Physician.

AESIs observed with MEDI4736 +/- tremelimumab include the following:

- Diarrhea / Colitis and intestinal perforation
- Pneumonitis / ILD
- Hepatitis/transaminase increases
- Neuropathy/neuromuscular toxicity (eg, Guillain-Barré, and myasthenia gravis)
- Endocrinopathy (ie, events of hypophysitis/hypopituitarism, adrenal insufficiency, and hyper- and hypothyroidism and type I diabetes mellitus)
- Rash / Dermatitis
- Nephritis / Blood creatinine increases
- Pancreatitis / serum lipase or amylase increases
- Myocarditis
- Myositis / Polymyositis
- Other inflammatory responses that are rare / less frequent with a potential immune-mediated aetiology include, but are not limited to, pericarditis, sarcoidosis, uveitis and other events involving the eye, skin, haematological and rheumatological events.

In addition, infusion-related reactions and hypersensitivity/anaphylactic reactions with a different underlying pharmacological aetiology are also considered AESIs.

Further information on these risks (eg, presenting symptoms) can be found in the current versions of the MEDI4736 and tremelimumab IBs. More specific guidelines for their

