All reported AEs will be listed along with the date of onset, date of resolution (if AE is resolved) and investigator's assessment of severity and relationship to study drug. Frequencies and percentages of patients reporting each preferred term will be presented (i.e. multiple events per patient will not be accounted for apart from any episode level summaries which may be produced).

Summary information (the number and percent of patients by system organ class and preferred term) will be tabulated for:

- All AEs
- All AEs causally related to study medication
- AEs with CTCAE grade 3 or 4
- AEs with CTCAE grade 3 or 4, causally related to study medication
- AEs with outcome of death
- AEs with outcome of death causally related to study medication
- All SAEs
- All SAEs causally related to study medication
- AEs leading to discontinuation of study medication
- AEs leading to discontinuation of study medication, causally related to study medication

- SAEs leading to discontinuation of study medication
- SAEs leading to discontinuation of study medication, causally related to study medication
- Immune mediated AEs based on pre-defined criteria presented in the immune mediated AE charter.
- Infusion reaction AEs

An overall summary of the number and percentage of patients in each category will be presented. In addition, a truncated AE table of most common AEs, showing all events that occur in at least 5% of patients in any treatment group will be summarized by preferred term, by decreasing frequency. This cut-off may be modified after review of the data. When applying a cut-off (e.g., 5%), the raw percentage should be compared to the cut-off, no rounding should be applied first (i.e., an AE with frequency of 4.9% will not appear if a cut-off is 5%).

Each AE event rate (per 100 patient years) will also be summarized by preferred term within each system organ class. For each preferred term, the event rate (defined as the number of patients with that AE divided by the total drug exposure of patients and then multiplied by  $365.25 \times 100$  to present in terms of 100 patient years) will be presented. For the MEDI4736 + tremelimumab arm, event rates will be based upon total combination duration including any tremelimumab re-treatment period (i.e. the very last dose date of study drug (MEDI4736 or tremelimumab) regardless of it being after tremelimumab re-started should be used as last dose in the calculation)

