### **Adverse events of special and possible interest**

Preferred terms used to identify adverse events of special interest (AESIs) and adverse events of possible interest (AEPIs) will be listed before database lock (DBL) and documented in the Study Master File. Grouped summary tables of certain MedDRA preferred terms will be produced and may also show the individual preferred terms which constitute each AESI/AEPI grouping. For each 'grouped' term, the number (%) of patients experiencing any of the specified terms will be presented by maximum CTCAE grade. Additional summaries will include Time to Onset of first CTCAE grade 3 or 4. Time to onset of first AE for each grouped term and preferred term within it will also be produced. Groupings will be based on preferred terms provided by the medical team prior to DBL, and a listing of the preferred terms in each grouping will be provided.

Additional summaries of the above-mentioned grouped AE categories will include number (%) of patients who have:

- At least one AESI/AEPI presented by outcome
- At least one AESI/AEPI causally related to study medication (as determined by the reporting investigator)
- At least one AESI/AEPI leading to discontinuation of IP

A summary of time to resolution to grade 1 or less and time to resolution to grade 2 or less will be provided.

Additionally, there will be several summaries of AESIs/AEPIs requiring concomitant treatment, and particularly the relationship of AESIs/AEPIs to the use of immunosuppressive agents (i.e., depicting which AESI/AEPI triggered immunosuppressive use) and, separately, to the use of immunosuppressive agents at high doses (High dose is defined as  $\geq 40$ mg of prednisone or equivalent per day).

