#### **Summary of long-term tolerability:**

To assess long term tolerability, provided that there are a sufficient number of patients with events to warrant it, prevalence plots, life table plots and cumulative incidence plots will be presented for each of the AESI grouped terms and any other events considered important after review of the safety data, provided there are  $\geq 10$  events, that is 10 events in at least one treatment group.

A prevalence plot provides information on the extent to which the events may be an ongoing burden to patients. The prevalence at time  $t$  after first dose of study treatment is calculated as the number of patients experiencing the event divided by the number of patients receiving study treatment or in safety follow-up at time  $t$ ; generally,  $t$  is categorized by each day after dosing. The prevalence will be plotted over time presented. Multiple occurrences of the same event are considered for each patient but a patient is only counted in the numerator whilst they are experiencing one of the occurrences of the event. These plots will only be produced for AESIs that have  $\geq 10$  events, that is 10 events in at least one treatment group.

For each AESI, median time to first onset of the AESI from the date of first dose will be presented in patients in the safety analysis. Patients who did not experience the AESI will be censored at the end of their safety follow-up. Summary tables of time to first onset for each AE will also be produced (e.g. 1-28 days, 29-56 days, 57-84 days, 85-112 days, >112 days). Median duration of the AE and AESI will be presented in patients who experienced each, as well as the median time to resolution to grade 1 or less and time to resolution to grade 2 or less.

A life table plot can be used to describe the time to onset of the event and specifically when patients are at most risk of first experiencing the event. The hazard, or in other words, the probability of having an AE in a specified time period (e.g. 0-1 months, 1-3 months, 3-6

months, etc.) given that the patient reaches that time period without having an event is plotted for each time period. These plots will only be produced for AESIs that have  $\geq 10$  events, that is 10 events in at least one treatment group.

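### The SAP's list of adverse events of special interest, given as the protocol's list, leaves out infusion-related and hypersensitivity/anaphylactic reactions (minor correction)

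*SAP*

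**What the plan says.** **Protocol 6.7.1** gives 11 bulleted AESI categories, all with a potential inflammatory or immune-mediated mechanism. It then adds: "In addition, infusion-related reactions and hypersensitivity/anaphylactic reactions with a different underlying pharmacological aetiology are also considered AESIs".

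**SAP 3.3.1 (AESIs)** attributes its list to the protocol, with AESIs that "have been identified in the CSP as Diarrhea/Colitis and intestinal perforation, Pneumonitis/ILD, hepatitis/transaminase increases" and so on. It ends with a residual category: "other inflammatory responses that are rare/less frequent with a potential immune-mediated aetiology including, but not limited to, pericarditis, sarcoidosis, uveitis" and similar events. There is no infusion-related, hypersensitivity or anaphylactic category. The July 2018 entry in the SAP amendment history says that the AESIs were brought into line with the protocol.

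**How the outputs are built.** SAP 4.2.13.1 states: "Groupings will be based on preferred terms provided by the medical team prior to DBL". SAP 3.3.1 also says: "A further review will take place prior to database lock to ensure new terms not already included in the older MedDRA version are captured". Under the long-term tolerability heading, plots "will be presented for each of the AESI grouped terms and any other events considered important after review of the safety data".

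**What else covers these events.** Among the system organ class and preferred-term tables, SAP 4.2.13.1 lists "Infusion reaction AEs". It has no matching item for hypersensitivity or anaphylaxis.

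**The concern.** The SAP presents its list as the protocol's, and the two do not match. The grouped AESI outputs give maximum grade by group, outcome, causality, discontinuation, time to onset and resolution, the link to immunosuppressant use, and the prevalence, life-table and cumulative incidence plots. A reaction type with no AESI category has no specified place in any of these.

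Grouping matters most for hypersensitivity/anaphylaxis. Such events can be coded to several preferred terms, and a preferred-term table does not show how many patients had at least one of them. The protocol treats both reaction types as real risks. Section 1.3.2.1 names infusion-related and hypersensitivity reactions for MEDI4736. Section 1.3.2.2 names infusion-related reactions, anaphylaxis and allergic reactions for tremelimumab. Section 6.7 requires sites to be equipped for anaphylaxis. The SAP does give infections and haemorrhage full output sets of their own, although neither is on the protocol's AESI list.

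**Working it through.** There is no figure to reproduce. The check compares the two lists item by item and then traces where the missing items could still be reported.

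**1. Category count.**

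| | Protocol 6.7.1 | SAP 3.3.1 |
|---|---|---|
| Bulleted categories (diarrhea/colitis through other rare inflammatory responses) | 11 | 11 |
| Infusion-related reactions | named as AESI | absent |
| Hypersensitivity/anaphylactic reactions | named as AESI | absent |

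The SAP has 11 of the 11 bulleted categories and 0 of the 2 added reaction types. Nothing else is missing.

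**2. Could another SAP category take them in?**
- The residual AESI category is limited to events with a potential immune-mediated aetiology. The protocol sets the two reaction types apart precisely because their aetiology is different.
- Adverse events of possible interest (AEPIs) are also defined by a potential inflammatory or immune-mediated basis, though one less likely than other causes. Some hypersensitivity terms might be placed there. The documents do not say so.
- The review before database lock is described as fitting new MedDRA terms into the existing categories, not as adding categories.

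**3. What is still reported under the SAP as written?**

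| Output | Infusion-related | Hypersensitivity/anaphylactic |
|---|---|---|
| Preferred-term tables: all, causally related, Grade 3 or 4, fatal, serious, leading to discontinuation; rate per 100 patient-years | yes | yes |
| Maximum CTCAE grade, time to first onset, duration and time to resolution for each AE | yes | yes |
| Dedicated table | one | none |
| Grouped AESI summaries, including immunosuppressant use | no category | no category |
| Prevalence, life-table and cumulative incidence plots | only if judged important after data review | only if judged important after data review |

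**4. Effect of adding the groups.** SAP 3.3.1 derives imAEs from AESIs and AEPIs by rules that look at systemic steroids, immunosuppressants and endocrine therapy. For AEPIs, the investigator's causality assessment or immune-mediated designation is considered first; no such step is described for AESIs. If the two groups were added with no further statement, a reaction treated with systemic steroids could be classed as immune-mediated, contrary to the aetiology given in the protocol.

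**The case against.** The strongest reply is that the prose list in SAP 3.3.1 does not itself produce the tables. A preferred-term list does; it is due before database lock, is filed outside the SAP, and is not available here. It may already contain both groups. The AESI tables are joint AESI/AEPI tables, so some hypersensitivity terms could enter as AEPIs. SAP 4.2.13 also allows extra safety tables, and the table of changes from the protocol is redacted, so a declared departure cannot be excluded. Most of what the grouped tables would show is already given by preferred term.

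Much of this stands, and it limits the consequence. A reader might infer that these reactions will be missing from every AESI output. The documents support only that the SAP text gives them no category. A reader might also take from Protocol 1.1.1 the "Grade 3 or 4 infusion-related reactions reported in 3% of patients" and turn it into an expected number of missed cases. That rate is historical, comes from the EXTREME arm of another study, and is described there as a cetuximab toxicity. It says nothing about the MEDI4736 arms, and such cases would still appear in the infusion-reaction and Grade 3 or 4 tables.

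The mismatch itself is not answered. The SAP cites the protocol as the source of its list and omits part of it. In an open-label trial, leaving the matter to an unseen list or to a choice made after looking at the data is weaker than one line in the SAP.

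**Conclusion.** The point holds as a minor correction. SAP 3.3.1 is wrong against the source that it cites: two AESI types named in Protocol 6.7.1 are absent, and no other SAP category clearly covers them. As written, neither has a place in the grouped AESI outputs. The loss is smaller for infusion-related reactions, which keep a dedicated table, than for hypersensitivity/anaphylaxis, which has no grouped output.

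This rests on two assumptions that cannot be checked here: that the pre-lock preferred-term list follows the SAP's stated categories, and that the redacted table of changes does not declare the omission as deliberate. SAP 4.2.13 plans no formal analysis of safety data, so no endpoint, power figure or alpha-controlled test is affected. Nor does the omission alter which events investigators must report, since Protocol 6.7.1 governs that.

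**What to change.** 1. In SAP 3.3.1, add *Infusion-related reactions* and *Hypersensitivity/anaphylactic reactions* as AESI groups, as in Protocol 6.7.1.
2. Add both groups to the preferred-term list held before database lock.
3. Run them through the grouped AESI summaries in SAP 4.2.13.1 for all three arms.
4. State that the two groups do not enter the imAE derivation by default, because the protocol gives them a different aetiology, and check that the imAE Charter agrees.

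If the omission was intended, state and justify the departure from Protocol 6.7.1 instead.

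The cost is a few lines of SAP text, a term list for each group, and two more groupings in existing table shells. No new data are needed.

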### **AEs of possible interest (AEPIs)**

Adverse events of possible interest (AEPIs) are AEs that also have a potential inflammatory or immune-mediated pathophysiological basis resulting from the mechanism of action of durvalumab and/or tremelimumab but are more likely to have occurred due to other pathophysiological mechanisms and, thus, the likelihood the event is inflammatory or immune-mediated in nature is not high and/or is most often or usually explained by the other causes. These AEs not routinely arising from an inflammatory or immune-mediated mechanism of action – typically quite general clinical terms that usually present from a multitude of other causes –are classified as AEPIs.

A framework of questions was developed by the Sponsor to identify event terms that may have an inflammatory or immune-mediated mechanism of action but implicitly have a lower likelihood of that than other causes and, thus, should be included as an AEPI not an AESI term.

### **Immune-mediated Adverse Events (imAE)**

Immune-mediated Adverse Events (imAE) will be identified from both AESIs and AEPIs based on programmatic rules that consider interventions involving systemic steroid therapy, immunosuppressant use, and/or endocrine therapy (which, in the case of AEPIs, occurs after first considering an Investigator's causality assessment and/or an Investigator's designation of an event as immune-mediated). Further details are provided in an imAE Charter v6.

In addition, the Sponsor may perform medical review of those AESIs and classify them as imAEs or not imAEs via an independent manual adjudication process.

### **Infection Adverse Events**

Infection is an identified risk for another anti-PDL1 drug atezolizumab and listed in the Warnings and Precautions of its US label. Infection AEs will be presented in the CSR.

### 3.3.2 Treatment exposure

Exposure will be defined separately for MEDI4736 monotherapy, MEDI4736 on the MEDI4736+ tremelimumab combination arm, tremelimumab on the MEDI4736+tremelimumab combination arm, and also separately for cetuximab, a platinum [carboplatin or cisplatin], and 5FU on the standard of care arm for the initial period of treatment and for the retreatment period as follows:

Total (or intended) exposure of MEDI4736 (monotherapy)

- Total (or intended) exposure is defined as the total treatment period from first dose date of study drug to earliest of “last dose date of study drug + 27 days” or death date or DCO.

Total (or intended) exposure of MEDI4736 (combination)

- Total (or intended) exposure is defined as the total treatment period from first dose date of study drug to the earliest of “last dose date of study drug + 27 days” or death date or DCO regardless of tremelimumab being re-started or not.

Total (or intended) exposure of tremelimumab (combination)

- Total (or intended) exposure is defined as the total treatment period from first dose date of study drug to the earliest of “last dose date of study drug + 27 days” or death date or DCO. This will include the sum of the duration in the 2 tremelimumab periods (i.e., initial period and re-treatment) but excluding the count of time between the 2 periods (for example, the duration would sum up to 6 months if they did 3 months in each case even if the 2 periods were separated by several months).

Actual exposure of MEDI4736/tremelimumab

- Actual exposure is defined as above, but excluding total duration of dose delays. Actual treatment duration for tremelimumab will be derived similarly as was done by total exposure, that by combining the periods of tremelimumab and summing up the delays in each period.

Total (or intended) exposure for the SOC regimens (cetuximab, a platinum [carboplatin or cisplatin], and 5FU)

- The total (or intended) exposure for the individual SOC regimens will be calculated according to the dose schedule required for each SOC regimen as follows:
  - (a) Cetuximab: Total (or intended) exposure is defined as the total treatment period from first dose date of study drug to the earliest of “last dose date of study drug + 6 days” or death date or DCO
  - (b) Platinum and 5FU: Total (or intended) exposure is defined as the total treatment period from first dose date of study drug to the earliest of “last dose date of study drug + 20 days” or death date or DCO

The total (or intended) exposure will also be summarised by combining the SOC treatments together. The following rules will be applied for SOC total

- Total (or intended) exposure is defined as the total treatment period from first dose date of study drug to the earliest of “last dose date of YY SoC drug + xx days” or death date or DCO, xx depends on whether the patient was still receiving platinum or 5FU, or only on cetuximab:
  - if last dose of cetuximab is  $\geq 14$  days after last dose of platinum and 5FU, then YY=cetuximab and xx= 6 days
  - if last dose of cetuximab is  $< 14$  days after last dose of platinum and 5FU, then YY=platinum and xx= 20 days

Actual exposure will not be calculated for SOC.

Dose reductions are not permitted per the CSP for the immunotherapy agents (MEDI4736 or MEDI4736+tremelimumab). The actual exposure calculation makes no adjustment for any dose reductions that may have occurred.

Exposure will also be measured by the number of cycles received. For the immunotherapy arms, a cycle corresponds to a 4-week treatment; for SOC, a cycle corresponds to a 3-week treatment. If a cycle is prolonged due to toxicity, this should still be counted as one cycle. A cycle will be counted if treatment is started even if the full dose is not delivered. Each immunotherapy agent will be measured in terms of number of doses given.

